Statistical Methods		
All statistical processing will be performed using SAS® unless otherwise stated. Statistical significance will be based on two-tailed tests of the null hypothesis resulting in p-values of ≤ 0.05 unless stated otherwise. Inferential testing will compare each active treatment group to the combined Vehicle treatment group. Comparisons will not be performed between active treatments. Efficacy analyses will be performed using the intent-to-treat (ITT) and per-protocol (PP) populations with the ITT population considered as primary. Safety analyses will be performed using the safety population.
 
For the dichotomized IGA, subjects will be considered a success if their IGA score is clear or almost clear and at least two grades less than Baseline. For those subjects for whom no Week 12 assessments are available, the last observation will be carried forward (LOCF) in order to provide a value for efficacy parameters that are missing, primarily due to missed visits. Additionally, a sensitivity analysis to estimate missing efficacy data will be based on estimation using the method of Markov Chain Monte Carlo (MCMC) independently for each treatment group. All hypotheses will be two-sided at an alpha level of 0.05.
 
Descriptive Statistics
 
Descriptive statistics will be presented for the efficacy data at each evaluation for the ITT and PP populations. Safety data will be summarized as indicated below for the safety population. Continuous

Name of Sponsor/Company: Novan, Inc.	Name of Finished Product: SB204	Name of Active Ingredient: NVN1000	Individual Study Table Referring to Part of the Dossier: Volume: Page:	(For National Authority Use Only)

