4.1.7 DISCONTINUATION/WITHDRAWAL PROCEDURES

A subject may voluntarily withdraw from study participation at any time. If the subject withdraws consent and discontinues from the study, the Investigator will attempt to determine the reason for discontinuation and record the reason in the subject's study records and in the study database. If a subject is withdrawn because of an AE, that AE should be indicated as the reason for withdrawal. In the event of early discontinuation, (i.e., prior to Week 12/Day 84 visit) and whenever possible, the subject should be asked to return to the study center to complete the Week 12/ET evaluations. Subjects who withdraw from the study will not be replaced.

If at any time during the study the Investigator determines that it is not in the best interest of the subject to continue, the subject will be discontinued from participation. The Investigator can discontinue a subject at any time if medically necessary. The Investigator may discontinue a subject's participation if the subject has failed to follow study procedures or to keep follow-up appointments. Appropriate documentation in the subject's study record and the study database regarding the reason for discontinuation must be completed.

All subjects who fail to return to the study center for the Week 12/ET visit will be contacted by telephone to determine the reason(s) why the subject failed to return for the necessary visit or elected to discontinue from the study. If a subject is unreachable by telephone after a minimum of two documented attempts (one attempt on two different days), a certified letter will be sent requesting that the subject contact the Investigator.

Reasons for an Investigator's withdrawal of a subject may include, but are not limited to, the following:

- Safety (e.g., severe adverse reactions, pregnancy);
- Lack of efficacy as determined by the Investigator;
- When the requirements of the protocol are not respected (e.g., significant issues with dosing compliance);
- When a concomitant medication or treatment likely to interfere with the results of the study is reported, or required, by the subject (the Investigator will decide, in consultation with QST, whether the subject is to be withdrawn);

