- When a subject is lost to follow-up. The Investigator will try twice to reach the subject by telephone and will send a certified follow-up letter before considering that the subject is lost-to-follow-up. These actions will be reported on the subject's study record and a copy of the follow-up letter maintained in the Investigator's file.

Refer to Section 6.7 for a discussion of criteria for discontinuation of individual subjects from the study.

All premature discontinuations and their causes must be carefully documented by the Investigator on the subject's study record and in the study database. In no case will a subject who has been assigned a study number and randomized into the study be replaced by another.

All Week 12/ET evaluations should be performed at the time of premature discontinuation. All data gathered on the subject prior to termination will be made available to QST and Novan.

Study completion or reason(s) for discontinuation as listed in the study record will be entered into the study database as follows:

- Completed
- Adverse Event
- Lack of Efficacy
- Withdrawal by Subject
- Physician Decision
- Protocol Violation
- Lost to Follow-Up
- Pregnancy
- Worsening of condition

- Other

Novan has the right to terminate or stop the study at any time. Should this be necessary, both QST and the Investigator will ensure that proper study discontinuation procedures are completed.

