6.7 DISCONTINUATION OF INDIVIDUAL SUBJECTS FROM THE STUDY

Subjects who develop intolerance to the product as defined by scores of 'severe' (3) on 2 or more categories of tolerability (erythema, scaling, dryness, pruritus, burning/stinging) shall be discontinued from the study.

Subjects with > 5.0% methemoglobin at any post-baseline visit will be discontinued from the study.

If a subject is determined to be pregnant prior to Week 12, the subject will be discontinued from the study but followed until term.

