7. STATISTICAL ANALYSIS

7.1 GENERAL CONSIDERATIONS

All statistical processing will be performed using SAS® version 9.3 unless otherwise stated. Statistical significance will be based on two-tailed tests of the null hypothesis resulting in p-values of ≤ 0.05 unless stated otherwise. Inferential testing will compare each active treatment group to the combined Vehicle treatment group. Comparisons will not be performed between active treatments. Efficacy analyses will be performed for the intent-to-treat (ITT) and per-protocol (PP) populations. Safety analyses will be performed using the safety population.

For the dichotomized IGA, subjects will be considered a success if their IGA score is clear or almost clear and at least two grades less than Baseline.

For those subjects for whom no Week 12 assessments are available, the last observation will be carried forward (LOCF) in order to provide a value for efficacy parameters that are missing, primarily due to missed visits. Additionally, a sensitivity analysis to estimate missing efficacy data will be based on estimation using the method of Markov Chain Monte Carlo (MCMC) independently for each treatment group. All hypotheses will be two-sided at an alpha level of 0.05.

A detailed description of the statistical methodology and data reporting for this study will be provided in the Statistical Analysis Plan (SAP). The SAP will be finalized before the database is locked and released to Novan. Any deviations from the SAP will be justified in the clinical study report.

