7.2.3 PER-PROTOCOL POPULATION

The PP population will include subjects who complete the Week 12 evaluation without noteworthy study protocol violations (i.e., any subject or investigator activity that could have possibly interfered with the therapeutic administration of the treatment or the precise evaluation of treatment efficacy). The PP population will include subjects in the safety population who do not meet any of the following criteria:

- Violated the inclusion/exclusion criteria;
- Have taken any interfering concomitant medications;
- Did not attend the Week 12 visit, with the exception of a discontinuation from the study due to an adverse event related to study treatment or documented lack of treatment effect;
- Have missed more than one interim study visit;
- Have not been compliant with the dosing regimen (i.e. subjects must apply 80-120% of the expected applications of study medication during participation in the study);

- Out of visit window at the Week 12 visit by ± 5 days;

Prior to breaking the blind, other additional criteria may be added to the list to accommodate for unforeseen events that occurred during the conduct of the trial that result in noteworthy study protocol violations.

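### The planned imputation is wrongly said not to need missing at random and appears to omit Baseline, while LOCF, the main rule for Week 12 lesion counts, can bias the difference either way

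*Protocol*

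**What the plan says.** **Main rule.** Section 7.1 and the synopsis (Statistical Methods) state that, if a subject has no Week 12 value, "the last observation will be carried forward (LOCF) in order to provide a value for efficacy parameters that are missing". The stated reason for the gaps is "primarily due to missed visits". The synopsis runs efficacy analyses on ITT and per-protocol sets, "with the ITT population considered as primary". ITT (7.2.1) requires randomization and dispensing only, not a post-baseline value. The lesion-count model (7.5) is an ANCOVA with treatment and baseline count.

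**Sensitivity analysis.** Section 7.1 adds that "a sensitivity analysis to estimate missing efficacy data will be based on estimation using the method of Markov Chain Monte Carlo (MCMC"), separately for each treatment group. Section 7.5.1 asserts that the method does not depend on missing at random. The code there is PROC MI with an `mcmc` statement, run within each of the five arms. The lesion-count list is `lescnt2-lescnt5`; the IGA list is `IGA1 IGA2 IGA4 IGA8 IGA12`.

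**Foreseen discontinuation.**
- Section 6.7: subjects scoring severe on two or more tolerability categories "shall be discontinued from the study"; a methemoglobin rule also applies.
- Section 4.1.7: reasons for withdrawal by the investigator include "Lack of efficacy as determined by the Investigator", and the recorded reasons include adverse event and worsening of condition.
- Section 7.2.3: the Week 12 attendance rule excepts "a discontinuation from the study due to an adverse event related to study treatment or documented lack of treatment effect".
- Section 4.1.7 also says "All Week 12/ET evaluations should be performed at the time of premature discontinuation".

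**The concern.** Three things are at stake, in this order.

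1. **A false description.** MCMC imputation under a multivariate normal model assumes that, given the variables in the model, missingness does not depend on the unseen values. Running it by arm makes that assumption arm-specific; it does not remove it. A reader who believes the sentence will take agreement between LOCF and imputation as evidence against informative dropout. The analysis cannot give that evidence.
2. **A probable gap in the imputation model.** If Baseline is missing from the lesion-count list, the imputation leaves out the covariate that the ANCOVA adjusts for. An ITT subject with no post-baseline count would then have no observed value in the model.
3. **The main rule itself.** LOCF treats an earlier count as the Week 12 count. That holds only if counts stop changing after the last visit. Several of the protocol's own reasons for stopping depend on treatment or response, so neither the amount nor the timing of dropout need be equal across arms. Three active regimens are each compared with one pooled vehicle group, so unequal dropout would distort the three estimates by different amounts.

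**Working it through.** **No plan figure to reproduce.** Section 7.8 gives no dropout rate, SD, effect size or power. The arm sizes agree with the ratio: 200 × 2/8 = 50 per active arm and 200 × 1/8 = 25 per vehicle arm, so 25 + 25 = 50 in the pooled vehicle group.

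**Does the list omit Baseline?** Table 2, footnote 1, makes Visit 2 the Week 2 visit, so Baseline would be visit 1. Four indices, 2 to 5, then match Weeks 2, 4, 8 and 12. The IGA list has five variables, and since there is no Week 1 visit, `IGA1` is presumably Baseline. The lesion-count list is one short. This is inference, because the `lescnt` index is not defined.

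**LOCF bias.** For one arm, bias = dropout share × (mean count at last visit − mean count at Week 12). The bias in the difference is active minus vehicle; a positive value works against active.

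Assumed inflammatory means at Baseline and Weeks 2, 4, 8 and 12: 28, 24, 21, 18, 16. The distances from Weeks 2, 4 and 8 to Week 12 are 8, 5 and 2. Dropouts' last visits are split over Weeks 2/4/8 in three assumed ways.

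With no true effect:

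| Timing | Gap per dropout | 20% v 10% (× 0.10) | 30% v 10% (× 0.20) |
|---|---|---|---|
| Early 50/30/20 | 0.5×8 + 0.3×5 + 0.2×2 = 5.9 | 0.59 | 1.18 |
| Even thirds | (8+5+2)/3 = 5.0 | 0.50 | 1.00 |
| Late 20/30/50 | 0.2×8 + 0.3×5 + 0.5×2 = 4.1 | 0.41 | 0.82 |

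Swapping the arms reverses the sign. Simulation (6,000 trials per cell, 50 v 50, Week 12 SD 10, ANCOVA on baseline) agrees: 0.41 to 0.58 and 0.83 to 1.21, with two-sided rejection of 5.4 to 6.5% and 8.1 to 10.9%. With equal dropout and no effect, bias was within 0.06.

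With a true effect of −5.0 (active 28, 22.5, 18.5, 14.5, 11), the active distances are 11.5, 7.5 and 3.5:
- Active gaps: early 0.5×11.5 + 0.3×7.5 + 0.2×3.5 = 8.7; late 0.2×11.5 + 0.3×7.5 + 0.5×3.5 = 6.3.
- 20% v 20%: −5.0 + 0.2×(8.7−5.9) = −4.44 (early); −5.0 + 0.2×(6.3−4.1) = −4.56 (late).
- 20% v 10%: −5.0 + 0.2×8.7 − 0.1×5.9 = −3.85 (early); −5.0 + 0.2×6.3 − 0.1×4.1 = −4.15 (late).
- 10% v 20%: −5.0 + 0.1×8.7 − 0.2×5.9 = −5.31 (early); −5.0 + 0.1×6.3 − 0.2×4.1 = −5.19 (late).

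**Response-related dropout.** In a simulated case with no effect, poor responders left at 11% on active and 26% on vehicle. LOCF gave −1.32 (favouring active); imputation by arm with Baseline gave −0.04.

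**A second set of assumed trajectories** (changes −4, −7, −10, −12; no effect). With dropout after Week 2 or Week 4 at 20% v 5%, the closed form is 0.15 × (12 − 5.5) = 0.975, and simulation gave 1.05. With poor responders leaving at 5% on active v 25% on vehicle, simulation gave −1.15.

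**Imputation by arm with Baseline.** Bias stayed within 0.1 lesion in the missing-at-random cells of the main set, and within 0.2 in the second.

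**Effect of omitting Baseline.** About 0.1 lesion at most in the second set. If only subjects with baseline above 28 drop out, the bias is −0.20 (20% v 10%) or −0.45 (30% v 10%), against 0.01 and 0.06 with Baseline included.

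**The case against.** **The sizes are assumed, and moderate cases are small.** This stands. A bias of 0.4 to 0.6 lesions is 0.04 to 0.06 of the assumed SD of 10.

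**Differential dropout is not shown.** This stands too. A reader might infer that LOCF will favour, or penalise, SB204 in this trial. Sections 1.4 and 1.5 report similar adverse event profiles on active and vehicle, so the documents support only a possibility. Nor is false-positive control the main issue, since section 7.5 disclaims multiplicity control.

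**Missed visits may indeed be the main source of gaps.** A reader might infer that the phrase is wrong. That is not supported: leavers are asked for the Week 12/ET evaluations, and if those values fill the Week 12 slot, most remaining gaps would be missed visits. But an early-termination value used as Week 12 acts much like LOCF. Taken halfway to the next visit, the gaps become 4.5, 3.7 and 2.85 lesions, or about 0.3 to 0.45 at 20% v 10%. How such visits are mapped belongs in the SAP.

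**Making a missing-at-random method primary is circular when dropout follows intolerance or poor response.** Partly right. No missing-not-at-random case was simulated, so the good performance of imputation is conditional. But observed counts carry much of the response information, and LOCF's assumption of no further change is harder to defend while counts fall. Null rejection with imputation was 2.9 to 4.3%, slightly conservative.

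**A delta-adjusted analysis is SAP detail.** Ordinarily yes. Here the protocol claims a property that its only sensitivity analysis lacks, so the gap comes from its own statement.

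**The IGA.** A reader might infer that its missing-data rule must change as well. Counting leavers as failures is a defensible composite, but it would give the co-primary endpoints different estimands. That is a trade-off, not an error to correct here.

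**Conclusion.** The sentence in 7.5.1 is false, whatever one thinks of LOCF. As written, the protocol contains no sensitivity analysis that tests departures from missing at random.

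The omission of Baseline from the lesion-count list is a sound inference but not certain. Its effect is probably small and is confined to the sensitivity analysis as planned. It matters more if the imputation becomes the main method.

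LOCF as the main rule is a poor choice rather than a demonstrated source of bias in this trial. If counts are still falling at dropout, the bias follows the arm that loses more subjects, so LOCF cannot be called reliably conservative. With balanced dropout there is no bias under no effect, but a true effect that is still growing is shrunk (−5.0 to about −4.4 to −4.6). The estimates of about 0.4 to 0.6 lesions at 20% v 10% and 0.8 to 1.2 at 30% v 10% rest on assumed trajectories, dropout rates and timing. They show direction and rough range only. The change should be made; confidence in its practical size is medium.

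**What to change.** 1. In 7.5.1, replace the sentence on missing at random with: *This method assumes data are missing at random given the values in the imputation model.*
2. Add the Baseline count to the lesion-count `var` statement, or confirm that it is already included.
3. In 7.1 and the synopsis, make this imputation by arm the main method for the two lesion-count endpoints, and keep LOCF as a sensitivity analysis.
4. Add one delta-adjusted sensitivity analysis for the lesion counts, so that the protocol has the check it claims.

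**Cost.** Wording and some programming. The imputation is already planned, and the visit data and discontinuation reasons are already collected.

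**Downsides.** The main lesion-count analysis then relies on missing at random, and each vehicle arm is imputed from about 25 subjects. Under the assumed inputs the standard error rises from about 1.75 to between 1.95 and 2.06. For a true −5.0, power goes from 56% to 71% with early dropout of 20% v 10%, but from 70% to 68% at 20% v 20%.

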7.2 POPULATIONS

7.2.1 INTENT TO TREAT (ITT) POPULATION

The ITT population will include all study subjects who were randomized and dispensed study medication.

7.2.2 SAFETY POPULATION

The safety population will include all randomized subjects with documented use of study medication (at least one application) and at least one post-baseline safety assessment.

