Study Design	This is a multi-center, evaluator-blinded, randomized, vehicle-controlled, parallel-group study to be conducted in approximately 200 subjects with acne vulgaris. Subjects who satisfy the entry criteria will be randomized to SB204 4% Gel BID, SB204 4% Gel QD, SB204 2% Gel BID, Vehicle Gel BID, or Vehicle Gel QD in a 2:2:2:1:1 ratio. The SB204 Gel and Vehicle Gel will be delivered from a double barrel single pump dispenser. The pump dispenses product from two chambers (NVN1000 Gel and a hydrogel or Vehicle Gel and a hydrogel) which will be mixed together in the palm for 5-10 seconds by the subject and applied to the entire face once or twice daily after washing. Efficacy assessments will include investigator global assessments (IGA) and inflammatory and non-inflammatory lesion counts. Tolerability and safety assessments include cutaneous tolerability evaluation (erythema, scaling, dryness, pruritus, burning/stinging), adverse event collection, physical exams, blood pressure and pulse rate, laboratory assessments including chemistry, hematology, methemoglobin, PT/ PTT measurements, and urine pregnancy tests (UPTs). Subjects will return for post-baseline evaluation at Weeks 2, 4, 8, and 12.		

Name of Sponsor/Company: Novan, Inc.	Individual Study Table Referring to Part of the Dossier:	(For National Authority Use Only)
Name of Finished Product: SB204	Volume:	
Name of Active Ingredient: NVN1000	Page:	

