Based on the known mechanism of action of nitric oxide, theoretical risks from systemic exposure following topical administration of NVN1000 Gel or SB204 Gel include hypotension and headache. Methemoglobinemia has been reported in patients treated with inhaled nitric oxide. Methemoglobin will be monitored during the study and treatment stopped in any subject with a measured methemoglobin > 5.0%.

Inadvertent administration to the eyes may result in ocular irritation and should be avoided. Should the product be accidentally instilled in the eye(s), prompt flushing with copious amount of normal saline or water is recommended.

A transient (approximately 5-10 minutes), asymptomatic erythema has been observed in some subjects shortly after application of NVN1000 Gel or SB204 Gel which is a physiologic response

(vasodilation) to local nitric oxide release. Topical application has been associated with local application-site reactions including erythema, peeling, desquamation, or burning/stinging. These local application-site reactions may occur due to the active agent (NVN1000) or the vehicle. Local application-site events including erosions and contact dermatitis were reported in subjects with psoriasis treated with NVN1000 Gel and Vehicle Gel under occlusion. These local application-site reactions resolved after discontinuation of the product and by the end of the study.

Based on available data, Novan anticipates that the risks to subjects enrolling in this Phase 2 study at which the maximum strength of SB204 Gel will be 4% twice daily to approximately 4 percent total body surface area are minimal, and that appropriate monitoring is in place to assess safety. At this stage of development, it is unknown if a clinical benefit will be observed in subjects with acne vulgaris following treatment for 12 weeks.

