4. STUDY PROCEDURES AND METHODS

4.1 SUBJECT ENTRY PROCEDURES

Prospective subjects as defined by the eligibility criteria in Sections 3.7.2 and 3.7.3 (Inclusion/Exclusion Criteria) will be considered for entry into this study. Subjects' informed consent/assent must be obtained prior to conducting any procedures.

Some Baseline procedures (i.e., review of inclusion / exclusion criteria, brief physical exam, methemoglobin assessment, blood pressure and pulse rate, IGA, lesion counts, cutaneous tolerability, adverse event assessment, concomitant medication review and UPT) must be completed prior to randomization. Subjects with clinically significant anemia as determined by the Investigator or methemoglobin values >3.0% will not be randomized.

WOCBP having a positive UPT at Screening or Baseline may not be randomized into the study. Women of childbearing potential must agree to use an effective form of contraception during participation in the study and for 30 days after their final study visit. Effective contraception is defined as stabilized on oral contraceptive for at least 3 months, IUD, condom with spermicide, diaphragm with spermicide, implant, NuvaRing®, medroxyprogesterone injection, transdermal patch or abstinence with a documented second acceptable method of birth control should the subject become sexually active. Females taking hormonal contraceptives must have taken the same type for at least three months (90 days) prior to entering the study and must not change type during the study. Subjects who had used hormonal contraception and stopped must have stopped no less than three months prior to the start of the study. Male subjects must agree to avoid fathering a child during the study and for 60 days after the last dose of the study drug by ensuring one of the acceptable methods of contraception is used and not donating sperm.

A female is considered to be of childbearing potential UNLESS she is post-menopausal (no menses for 24 consecutive months), surgically sterilized, or without a uterus and/or both ovaries.

After the required procedures are completed and study eligibility is confirmed, the subject will be randomized to treatment utilizing an IWRS which will identify the study drug pump to be dispensed to the subject. The subject will be trained on the mixing, application, and storage of the study drug. All study drug applications will be done at home.

Table 2: Schedule of Visits and Procedures

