4.1.3 WEEK 2 (DAY 14)

The following procedures must be performed and recorded at the Week 2 visit:

1. Update concomitant medication information.
2. Update AE information and record any new AEs if applicable.
3. Measure percent methemoglobin.
4. Collect blood pressure and pulse rate.
5. Perform IGA.
6. Perform lesion counts.
7. Perform cutaneous tolerability evaluation.
8. Collect returned study drug and diary, perform accountability, and review study drug compliance with subject.
9. Review subject diary for completion.
10. Dispense new study drug and diary if needed.
11. Review and confirm the study schedule with the subject.

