7.4 DESCRIPTIVE STATISTICS

Descriptive statistics will be presented for the efficacy data at each evaluation for the ITT and PP populations. Safety data will be summarized as indicated below for the safety population.

Continuous data will be summarized with sample size (N), mean, median, standard deviation, minimum and maximum. Categorical data will be summarized with N, frequency counts, and percentages.

Descriptive statistics will be presented for the active treatment groups, each vehicle treatment group, and the vehicle treatment groups combined.

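### Safety-population membership depends on a post-baseline safety assessment, so treated subjects who never return can be left out of the summary adverse-event tables and denominators

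*Protocol*

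**What the plan says.** Section 7.2.2 places two conditions on randomized subjects before they enter the safety population: "with documented use of study medication (at least one application) and at least one post-baseline safety assessment". Section 7.1 then states "Safety analyses will be performed using the safety population", and Section 7.4 repeats this for the descriptive output: "Safety data will be summarized as indicated below for the safety population".

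The design separates exposure from assessment. Section 4.1 says "All study drug applications will be done at home". The synopsis says "Subjects will return for post-baseline evaluation at Weeks 2, 4, 8, and 12", so the first scheduled look at a treated subject is Day 14. Evidence of use comes back at that same visit, where Section 4.1.3 tells staff to "Collect returned study drug and diary, perform accountability, and review study drug compliance with subject".

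Section 4.1.7 asks early discontinuers to return for the Week 12/ET evaluations where possible. Subjects who miss that visit are telephoned for the reason and sent a certified letter if they cannot be reached. Section 7.7.1 lists all AEs by subject and lists subjects who stop because of an AE.

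**The concern.** The assessment condition is met or missed after randomization, and early intolerance can be the reason it is missed. Section 1.5 names "local application-site reactions including erythema, peeling, desquamation, or burning/stinging" as effects associated with topical application. A subject who reacts in the first two weeks, stops and does not come back has been exposed but may have no visit-based assessment. Under Section 4.3.1 a tolerability finding becomes an AE if it is severe or leads to discontinuation, so this subject's reaction is one that should be reported.

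Tolerability and safety are part of the primary objective (Section 2.2), and the comparison of AEs between groups is a safety endpoint (Section 3.1.3). If such subjects leave both the count of events and the count of subjects at risk, early intolerance can be understated, and the comparison can be distorted if this happens more in one group than another. The ITT population in Section 7.2.1 has no post-baseline condition, so the same subject can count for efficacy but not for safety.

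**Working it through.** The protocol states no dropout rate or early-reaction rate, so there is no figure of its own to reproduce beyond the arm split in Section 7.8. That split checks: 200 × 2/8 = 50 per active arm and 200 × 1/8 = 25 per vehicle arm.

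**Step 1. Can a treated subject fail the definition?** Dosing starts at home after Baseline, and no visit is scheduled before Day 14. A subject who attends nothing after Baseline has no post-baseline vital signs, methemoglobin, tolerability or laboratory reading. The only possible post-baseline safety information is an AE reported by telephone.

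**Step 2. Does a telephoned AE count as an assessment?** The documents point both ways.
- For: AE collection is the first item under Section 4.4 (Safety Assessments), and the synopsis includes it among the tolerability and safety assessments. Section 6.2 requires every AE the subject reports to be recorded.
- Against: Section 6.2 describes AE assessment at scheduled visits, and Section 7.2.2 does not mention telephone reports.

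**Step 3. Does the subject meet the other condition?** Drug and diary are first collected at Week 2. A subject who never returns may therefore also lack documented use, whatever is decided about assessments.

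**Step 4. Size if recorded reactors are treated as unassessed.** Let n = 50 treated, s = reactors who were assessed, k = reactors excluded. The rate among all treated is (s + k)/n. The rate under the definition is s/(n − k). Both s and k are assumptions; s = 2 here.

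| k | All treated | Under the definition | Difference (points) |
|---|---|---|---|
| 1 | 3/50 = 6.0% | 2/49 = 4.1% | 1.9 |
| 2 | 4/50 = 8.0% | 2/48 = 4.2% | 3.8 |
| 3 | 5/50 = 10.0% | 2/47 = 4.3% | 5.7 |
| 5 | 7/50 = 14.0% | 2/45 = 4.4% | 9.6 |

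That is about 2 percentage points per excluded reactor.

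**Step 5. How likely is at least one such subject in an arm of 50?** The chance is 1 − (1 − p)^50, with p assumed. For p = 1%, 2% and 5% it is 0.395, 0.636 and 0.923.

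**Step 6. Size if the non-returners have nothing on record.** Suppose 5 of 50 react, 2 of them never return, and their reactions are never learned. The definition gives 3/48 = 6.3%. Restoring the 2 subjects gives 3/50 = 6.0%, because they add to the denominator only. No population definition recovers 5/50 = 10.0% in this case.

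**The case against.** The strongest reply is that the protocol itself treats AE collection as a safety assessment. On that reading, a reaction learned by telephone keeps the subject in, provided use is documented. Those excluded by the assessment condition are then the ones about whom nothing is known, and leaving them out raises the shown rate slightly rather than lowering it (Step 6). This stands as a plausible reading. It does not settle the matter, because Section 7.2.2 does not adopt it.

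The follow-up effort in Section 4.1.7 and the listings in Section 7.7.1 also stand: such subjects need not vanish from the report. Listings do not, however, supply rates or a comparison between groups.

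A reader might infer that the rule certainly removes subjects who react at home, and that a true 10.0% would be shown as 6.3% (5/50 against 3/48). The documents do not support that. The fall arises only if reactions on record are nevertheless classed as unassessed, and the counts are invented for illustration. Nor is there evidence that the effect would differ between active and vehicle: Section 1.4 reports similar AE profiles for the two in completed studies.

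**Conclusion.** The point holds as a low-cost improvement to a rule the protocol has already fixed. As written, Section 7.2.2 can leave treated subjects who never return out of the summary AE tables and denominators, and it does not say whether a telephoned AE prevents this. A bias in the safety results is possible but not shown.

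The number affected is probably small. The figure of about 2 percentage points per excluded reactor in an arm of 50 assumes that the reaction is on record and the subject is still treated as unassessed. Where nothing is on record, restoring the subject lowers the rate slightly. The effect on the per-protocol population should be small, since that set generally requires Week 12 attendance; the ITT population is not affected.

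**What to change.** In Section 7.2.2, define the safety population as all randomized subjects who applied study medication at least once, and delete the condition on a post-baseline safety assessment.

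That deletion is not enough alone, because of the documented-use condition. Add one of two rules: accept use reported by telephone as documented use, or presume use in anyone dispensed drug unless non-use is documented.

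State further that these subjects count in the AE and discontinuation denominators, that any AE reported by telephone enters the summaries, and that absent laboratory, vital-sign, tolerability and methemoglobin readings are shown as missing.

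The cost is a few sentences, with no new visits or data. The drawback is that presuming use may add a few subjects with no recorded safety data to the denominator, which slightly dilutes the rates. Reporting their number by arm lets the reader see how much.
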